4.2 Definition of Dose Limiting Toxicity

For the phase I portion, patients will be monitored for safety by assessing toxicities as graded by the NCI CTCAE v4.0. The maximum tolerated dose (MTD) or dose limiting toxicity (DLT) will be defined as one or more of the following toxicities considered to be at least possibly related to one of the study drugs during Cycle 1:

- Grade 3 or greater non-hematologic toxicity with the exception of Grade 3 nausea, vomiting and diarrhea that responds to supportive therapy.
- Grade 4 thrombocytopenia, or grade 3 thrombocytopenia with bleeding, or any requirement for platelets transfusion

- Grade 4 neutropenia persisting for more than 5 days.
- Grade 3 or greater febrile neutropenia (temperature $\geq 38.5^{\circ}\text{C}$)
- Grade 4 anemia, unexplained by underlying disease

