4.3 Dose Escalation/De-escalation

If a DLT occurs in 2 or more patients on a dose level during the first cycle, the MTD will be exceeded and we will consider this dose level to be intolerable. If a DLT occurs in 1 of 3 patients during this time, an additional 3 patients will be enrolled at that dose level cohort and evaluated for DLT before dose escalation can proceed. If no other patient in the cohort has a DLT, escalation to the next cohort may proceed 1 week later from the last included patient on the current cohort. If a second patient in a cohort has a DLT, MTD determination will then be conducted by one of the following schemes:

- If ≥ 2 of 3 patients in cohort 1 exhibit a DLT at the dose of 1.5 mg/kg CT-011 in combination with lenalidomide 15 mg, 3 more patients will be enrolled at a de-escalated dose level cohort. This de-escalation cohort (Cohort -1) will use the same dose of CT-011 (1.5 mg/kg) in combination with 10 mg lenalidomide. If no further DLTs are observed, we will consider dose escalation of the CT-011 with this lower dose of lenalidomide such that the dose escalation of CT-011 to 3 mg/kg with lenalidomide 10 mg will proceed in the next cohort. However, if ≥ 2 patients experience DLT with CT-011 1.5 mg/kg and lenalidomide 10 mg, then we will further de-escalate lenalidomide to 5 mg and enroll 3 more patients on CT-011 1.5 mg/kg combined with lenalidomide 5 mg. The same criteria for MTD will be used for these de-escalation dose level cohorts.
- If ≥ 2 patients in cohort 2 exhibit a DLT at the dose of 3 mg/kg CT-011 in combination with lenalidomide 15 mg, we will explore tolerability of an intermediate dose level of lenalidomide, where 3 patients will be enrolled and treated with 3 mg/kg of CT-011 in combination with 10 mg lenalidomide. The dose escalation of CT-011 to 6 mg/kg with lenalidomide 10 mg will proceed in the next cohort if no more than one DLT is observed in the 3 mg/kg CT-011+10mg lenalidomide cohort.
- If ≥ 2 patients in cohort 3 exhibit a DLT at the dose of 3 mg/kg CT-011 in combination with lenalidomide 25 mg, 3 more patients will be enrolled at the 3 mg dose of CT-011 in combination with 15 mg lenalidomide. If there is < 1 DLT with CT011 3mg/kg and lenalidomide 15 mg, this will be defined as the MTD. If there are 2 or more DLT, then 3 additional patients will be enrolled at the CT-011 3mg/kg and lenalidomide 10 mg, which will become the MTD.

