5.1.3 Route and Method of Administration

CT-011 will be administered intravenously on day 3 of a 28 day cycle.

CT-011 is to be administered intravenously using a peripheral line or a central device if such has been inserted. Patients will be dosed on a mg/kg basis.

The first time CT-011 is to be administered intravenously at a dose of 1.5/3.0/6.0mg/kg delivered over approximately 2 hours as follows:

1. Initial rate of infusion is 50 mL/hr for 30 minutes; If no symptoms related to infusion appear:
2. Increased rate to 100 mL/hr; for 30 minutes; If no symptoms appear:
3. Increased rate to 150 mL/hr for 30 minutes; If no symptoms appear:
4. Increase rate to 200 mL/hr for 30 minutes;

In the event that Grade 3 or higher infusion-related toxicity occurs during infusion, administration of CT-011 should be stopped immediately. Administration of CT-011 could be resumed only after the toxicity has resolved using the slowest rate of infusion (50mL/hr). Once the infusion is resumed, vital signs will be checked every 15 minutes for the first hour, then every 30 minutes till the end of the infusion and then one hour from end of infusion.

If no drug related or infusion related adverse events occur during the first administration, further CT-011 administrations could be delivered over approximately 1:15 hours at a rate of 200mL/hr. Subsequent administrations should be made as scheduled in the absence of Grade 3 or higher adverse events or disease progression.

The maximal administration rate is approximately 250 mg/hr. The total dose administered and the dosing rate will be documented in the patient's medical records.

To ensure complete delivery of CT-011, the IV infusion line must be flushed with 0.9% sodium chloride. The following are two recommended methods for flushing the CT-011 IV infusion line:

- 1) When the CT-011 infusion is complete, add an additional 50mL of 0.9% sodium chloride for

injection to the CT-011 infusion bag. Continue the infusion until a volume equal to that of the volume contained in the tubing has been administered.

- 2) Replace the empty CT-011 infusion bag with a 50mL bag of 0.9% sodium chloride for injection and infuse a volume equal to the volume contained in the tubing. Please note: the flush is not included in the total recommended infusion times.

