5.2 Lenalidomide (RevlimidTM)

5.2.1 Lenalidomide Administration and Schedule

Lenalidomide will be given orally. Schedule as shown in table 5.1

The first dose level starts at 15 mg days 1-21 of a 28 day cycle.

If a dose is missed or vomited up, the dose will not be made up.

Beginning by day 1 of cycle #2 and on day 1 of every cycle thereafter, while all six conditions below have been met, patients will be evaluated for lenalidomide dose escalation.

For patients that:

- Never had a lenalidomide dose reduction due to a toxicity that was probable or definitely related to lenalidomide.
- Maintained platelet count $\geq 50,000$ at all times in the previous cycle
- Minimum ANC $\geq 1,000$ at all times in the previous cycle
- No clinically significant grade 2 or greater non-hematologic toxicities in the previous cycle
- Not yet reached the maximum daily dose of 25 mg of lenalidomide
- Are willing to undergo dose escalation of lenalidomide.
- Serum Creatinine maintained at ≤ 2 mg/dL as in initial eligibility

Then the patient's dose for lenalidomide will be increased by 5 mg per cycle for days 1-21 of a 28 day cycle. If any of the criteria are not met, then no lenalidomide dose escalations will occur during this cycle.

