5.2.2 Lenalidomide dose levels

Before each drug dose, the patient will be evaluated for possible toxicities that may have occurred after the previous dose(s). Toxicities are to be assessed according to the NCI Common Terminology Criteria for Adverse Events (CTCAE), Version 4.0. Dose modifications or delays will be done based on the toxicity experienced during a cycle of therapy or newly encountered on day one of a cycle.

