5.8.6 Schedule of Events^a

Investigations	Screening	C1D3	C1D4	C1D6	C1D10	C1D17	C2D3	C3D3	C5D3	CxD3	End of Tx ^b	Follow Up ^p
History, physical examination, concomitant medication review	X	X					X	X		X	X	
Informed written consent	X											
Confirmation of disease relapse and prior treatment	X											
Skeletal survey (CT or MRI as clinically indicated) ^c	X										X	
MUGA or ECHO	X											
β-hCG ^d	X	X										
Toxicity evaluation	X	X					X	X		X	X	X
CBC / differential / platelets ^e	X	X					X	X	X	X ^f	X	
PTT, INR, TSH ^e	X											
BMP, glucose, magnesium ^e	X	X					X	X		X		
LFTs	X	X					X	X		X		
Beta 2 microglobulin ^g	X							X			X	
12-lead ECG ^h	X							X				
Serum monoclonal protein assessments ⁱ	X	X ⁱ					X ⁱ	X ⁱ		X ⁱ	X ⁱ	
24hr urine for creatinine clearance	X											
24hr urine monoclonal protein and immunofixation ^j	X	X ^j					X ^j	X ^j		X ^j	X ^j	
BM biopsy, unilateral ^k	X								X ^k		X ^k	
CT-011 Given		X					X	X	X	X		
Prescribe lenalidomide via RevAssist ^l	X											
T-cell, NK-cell, and CD14 Correlative studies ^m	X	X	X	X	X	X	X	X	X	X	X	X

CT-011 PK ⁿ		X	X	X	X	X	X				
ADA (immunogenicity) ^o	X										

- a. With the exception of PK samples, all other time points have a +/- 4 day window to accommodate weekends, holidays, and for patient convenience.
- b. Off study correlates will be done. In addition, continued T-cell correlate will be done at 1,3, and 6 months after removal from study
- c. Skeletal survey will be done at baseline and may be done at evidence of progression of disease. CT scan will be done to document size of plasmacytoma if this is the only measurable disease.
- d. Female patients of childbearing potential (FCBP, defined in section 8.5) must have a negative pregnancy test (β -hCG) as required by the RevAssist program. Lenalidomide and dexamethasone will start on day 1 of each cycle. Patients do not need to be in clinic to initiate this as all patients would have been exposed to both. Lenalidomide will be ordered for the next cycle. A pregnancy test (urine or serum β -HCG) will also be ordered at this time. Patients must have a negative β -HCG result prior to starting lenalidomide on day 1 of each cycle.

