- e. CBC d/p will be monitored biweekly in cycles 1 to 4, then monthly thereafter. Chemistry tests, including electrolytes, glucose and serum creatinine, should be performed every 2 weeks during the first 2 months of therapy and once a month thereafter. Serum electrolyte monitoring should include potassium, magnesium and calcium. PTT, INR and TSH will be checked every 2 months.
- f. CBC/d/p should also be checked on day 17 of a cycle where lenalidomide's dose has been escalated.
- g. Beta 2 microglobulin will be done after every 2 cycles and at evidence of progression of disease.
- h. Baseline and periodic ECGs should be performed during treatment as indicated in the flow chart. In patients who have ECG abnormalities, ECGs should be performed more routinely as clinically indicated. ECGs post-baseline should be performed as indicated
- i. Myeloma monoclonal protein assessments (Serum protein electrophoresis & immunofixation, immunoglobulin levels, serum free light chain assay) will be performed on day 3 of each cycle (when patients come in for CT-011 infusion) as well as off study.
- j. 24hr urine monoclonal protein assessment (Urine protein electrophoresis & immunofixation) will be performed at screening and as required for response assessment.
- k. Unilateral bone marrow (BM) biopsy will be done at baseline and at end of 4th cycle and evidence of progression for patients with non secretory multiple myeloma
- l. Lenalidomide must be prescribed through and in compliance with Celgene's RevAssist® program. Prescriptions must be filled within 7 days. Any unused lenalidomide should be returned to the patient for disposition in accordance with the RevAssist® program.
- m. T-cell, NK-cell, and CD14 correlates will be collected prior to CT-011 dosing on C1D3, C1D4, C1D6, C1D10, C1D17 and then on Day 3 of all subsequent cycles. T-cell correlates only will also be collected at 1, 3, and 6 months after discontinuation of protocol therapy.
- n. Samples for CT-011 PK determination will be collected in cycle 1 prior to CT-011 infusion, immediately at the end of the infusion, 1 hour after end of infusion, approximately 24(C1D4), 72(C1D6), 168 (C1D10) & 336 (C1D17) hrs – and just prior to next (cycle 2) infusion. Off-study correlates should be obtained at the time the patient is removed from protocol for any reason.

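### No liver test is scheduled between the Cycle 1 CT-011 infusion and day 31, so a silent Grade 3 or higher hepatic rise could go uncounted as a Cycle 1 DLT

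*Combined protocol and SAP*

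**What the plan says.** Section 4.2 limits DLTs to Cycle 1 and includes "Grade 3 or greater non-hematologic toxicity with the exception of Grade 3 nausea, vomiting and diarrhea that responds to supportive therapy", if at least possibly related to a study drug. Liver enzymes and bilirubin are not excepted. Escalation depends on these first-cycle events (Section 4.3).

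In the schedule of events (Section 5.8.6), the liver function row is marked at screening, C1D3, C2D3, C3D3 and later day-3 visits. It is blank at C1D4, C1D6, C1D10 and C1D17. Three other laboratory rows (blood count; PTT/INR/TSH; basic metabolic panel with glucose and magnesium) carry note e; the liver row does not. Note e reads in part: "Chemistry tests, including electrolytes, glucose and serum creatinine, should be performed every 2 weeks during the first 2 months of therapy". It names no liver analyte. Note a adds that, PK samples excepted, "all other time points have a +/- 4 day window".

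On timing, Section 4.3 says "escalation to the next cohort may proceed 1 week later from the last included patient on the current cohort". Section 5.2.1 sets a lenalidomide escalation check by day 1 of Cycle 2, one condition being "No clinically significant grade 2 or greater non-hematologic toxicities in the previous cycle". Note d says of the day 1 start: "Patients do not need to be in clinic to initiate this as all patients would have been exposed to both".

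**The concern.** A DLT that shows only in a blood test can be counted only if the test is done. Blood counts have a repeat schedule during Cycle 1; liver tests do not. A Grade 3 or higher rise without symptoms could therefore appear and resolve unseen. It could also be seen first at C2D3, after lenalidomide has restarted on day 29, and be dated to Cycle 2. No rule assigns such a finding to Cycle 1.

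In a 3+3 design one patient can change the decision. An error would carry forward: phase II is dosed at the MTD, reuses the 6 phase I patients treated there and adds 23 more (Sections 5 and 6.1.2). The protocol also gives a reason to look at the liver. Section 1.4.3 reports one Grade 4 hepatitis among three serious events of potentially immunological cause in the melanoma study.

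**Working it through.** The plan states no figure to reproduce here; the check is day arithmetic on the schedule.

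**Inputs**
- Cycle of 28 days, CT-011 on day 3 (Section 5.1.3).
- DLT window: Cycle 1, days 1 to 28 (Section 4.2).
- Liver test marks and the 4-day tolerance (Section 5.8.6, note a).
- Assumptions: Cycle 2 starts on time, and the C1D3 liver sample is drawn on the infusion day.

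**1. Next liver test after the infusion.** C2D3 = 28 + 3 = day 31. That is 31 − 3 = 28 days after the infusion and 31 − 28 = 3 days after the DLT window. Nominal post-infusion liver tests inside Cycle 1: 0.

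**2. Effect of the visit tolerance.** C2D3 may fall from 31 − 4 = day 27 to 31 + 4 = day 35, which is 9 permitted days. Only days 27 and 28 lie in Cycle 1, so 2 of the 9. This is a count of allowed days, not a probability. Nothing requires the early days.

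**3. Lenalidomide check for Cycle 2.** Day 1 of Cycle 2 is 28 + 1 = day 29. The same two early days are the only permitted C2D3 dates before it. Because a patient may start that cycle away from the clinic, the check can be passed with no post-infusion liver result.

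**4. Does note e fill the gap?** The metabolic panel row and the liver row have the same visit marks, but only the former carries note e. The analytes that the note names are electrolytes (potassium, magnesium and calcium), glucose and creatinine. A site may add liver tests; it is not told to.

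**5. Effect of one uncounted DLT under the 3+3 rule**

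| True count | Recorded count | Decision changes from | To |
|---|---|---|---|
| 1/3 | 0/3 | enroll 3 more at this level | escalate |
| 2/6 | 1/6 | exceeds the MTD | tolerable |

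**6. With liver tests at C1D10 and C1D17.** These fall 10 − 3 = 7 and 17 − 3 = 14 days after the infusion. Successive gaps are 7, 7 and 31 − 17 = 14 days, so the longest is 14 instead of 28. With the 4-day tolerance the tests fall on days 6–14 and 13–21, all within Cycle 1.

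**The case against.** Four points can be made for the plan.

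- **Other safeguards exist.** Toxicity is reviewed at each visit (Section 5.8.2) and before each dose (Section 5.2.2). For CT-011, "Subsequent administrations should be made as scheduled in the absence of Grade 3 or higher adverse events or disease progression". The oversight committee and monthly calls add review. These make it likely that symptomatic or persistent hepatitis would be found, and they partly protect the second infusion. None requires a liver result. The start-of-cycle criteria (Section 5.6) name no liver test, and the dose-adjustment table (Section 5.3.1) has no hepatic row.
- **The cohort decision may come after day 31.** Section 6.1.1 requires DLT evaluation before escalation. If the one-week wait follows that evaluation, the decision falls at about 28 + 7 = day 35, and a rise persisting at a day-31 test would be known. That is a fair reading. If the week runs from the last patient's inclusion, evaluation can end on day 28 and the decision can precede the test.
- **The scenario is narrow.** With the half-life of 270 to 410 hours in Section 1.4.2, day 31 is 672 hours after infusion, or 672/410 = 1.6 to 672/270 = 2.5 half-lives. CT-011 is still present, so full resolution of an immune-mediated rise by then is less likely. This is an inference, and it does not settle how a rise first seen at C2D3 is dated.
- **The hepatic signal is weak.** The hepatitis has no denominator or stated attribution, and the adverse event tables list no hepatic event. The lymphoma post-transplant table filters only events confined to Grades 1–2, so Grade 3 or higher events should appear. Zero among the 69 patients with any event gives a one-sided 95% upper bound of 1 − 0.05^(1/69) = 4.2%. That study gave CT-011 without lenalidomide in another disease, so the bound is indirect.

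It is also fair that the day-29 check concerns one patient's dose and cannot alter a Cycle 1 DLT count. It matters for safety only.

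**Conclusion.** The concern holds. As written, the plan requires no post-infusion liver test inside the DLT window, although a related Grade 3 or higher hepatic rise in that window is a DLT. This conclusion does not depend on the hepatic event rate. It rests on reading note e as not covering liver tests, which the missing note letter and the named analytes support.

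The effect on the MTD cannot be quantified from the documents. The exposed case is an asymptomatic Grade 3 or higher rise that either resolves before C2D3 or is first seen there and dated after day 28. Any resulting bias favors escalation. Given the narrow scenario and weak signal, this is a change that should be made because it is cheap and improves DLT ascertainment; it is not a fundamental flaw in the design.

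**What to change.** - Attach note e to the liver function row and name AST, ALT, bilirubin and alkaline phosphatase in it.
- Mark liver tests at C1D10 and C1D17, where blood is already drawn for PK and correlative work. PK samples are exempt from the 4-day tolerance, so a shared draw would only hold the liver test closer to its nominal day.
- Require a post-infusion liver result before a patient is classed as DLT-free and before the day-29 lenalidomide increase. Before the second infusion, require the result of a pre-dose C2D3 sample, drawn early enough to be reported.
- State whether a Grade 3 or higher rise in that pre-dose C2D3 sample counts as a Cycle 1 DLT.

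The cost is a few routine assays per patient on existing draws and a schedule amendment. Waiting for the C2D3 result could slightly delay the second infusion or the cohort decision.

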4.3 Dose Escalation/De-escalation

If a DLT occurs in 2 or more patients on a dose level during the first cycle, the MTD will be exceeded and we will consider this dose level to be intolerable. If a DLT occurs in 1 of 3 patients during this time, an additional 3 patients will be enrolled at that dose level cohort and evaluated for DLT before dose escalation can proceed. If no other patient in the cohort has a DLT, escalation to the next cohort may proceed 1 week later from the last included patient on the current cohort. If a second patient in a cohort has a DLT, MTD determination will then be conducted by one of the following schemes:

- If ≥ 2 of 3 patients in cohort 1 exhibit a DLT at the dose of 1.5 mg/kg CT-011 in combination with lenalidomide 15 mg, 3 more patients will be enrolled at a de-escalated dose level cohort. This de-escalation cohort (Cohort -1) will use the same dose of CT-011 (1.5 mg/kg) in combination with 10 mg lenalidomide. If no further DLTs are observed, we will consider dose escalation of the CT-011 with this lower dose of lenalidomide such that the dose escalation of CT-011 to 3 mg/kg with lenalidomide 10 mg will proceed in the next cohort. However, if ≥ 2 patients experience DLT with CT-011 1.5 mg/kg and lenalidomide 10 mg, then we will further de-escalate lenalidomide to 5 mg and enroll 3 more patients on CT-011 1.5 mg/kg combined with lenalidomide 5 mg. The same criteria for MTD will be used for these de-escalation dose level cohorts.
- If ≥ 2 patients in cohort 2 exhibit a DLT at the dose of 3 mg/kg CT-011 in combination with lenalidomide 15 mg, we will explore tolerability of an intermediate dose level of lenalidomide, where 3 patients will be enrolled and treated with 3 mg/kg of CT-011 in combination with 10 mg lenalidomide. The dose escalation of CT-011 to 6 mg/kg with lenalidomide 10 mg will proceed in the next cohort if no more than one DLT is observed in the 3 mg/kg CT-011+10mg lenalidomide cohort.
- If ≥ 2 patients in cohort 3 exhibit a DLT at the dose of 3 mg/kg CT-011 in combination with lenalidomide 25 mg, 3 more patients will be enrolled at the 3 mg dose of CT-011 in combination with 15 mg lenalidomide. If there is < 1 DLT with CT011 3mg/kg and lenalidomide 15 mg, this will be defined as the MTD. If there are 2 or more DLT, then 3 additional patients will be enrolled at the CT-011 3mg/kg and lenalidomide 10 mg, which will become the MTD.
- If ≥ 2 patients in cohort 4 exhibit a DLT at the dose of 6 mg/kg CT-011 in combination with lenalidomide 25 mg, 3 more patients will be enrolled at the 6 mg dose of CT-011 in combination with 15 mg lenalidomide. If there is < 1 DLT with CT011 6mg/kg and lenalidomide 15 mg, this will be defined as the MTD. If there are 2 or more DLT, then 3 additional patients will be enrolled at the CT-011 6mg/kg and lenalidomide 10 mg, which will become the MTD

To determine dose escalation, we will focus on the number of patients who experience dose limiting toxicity; i.e. a patient who experiences more than one DLT will be counted only once.

Discontinuation of treatment due to disease progression will not constitute a DLT.

In the Phase 1 portion of the study, subjects who withdraw or prematurely discontinue treatment before completing the first treatment cycle for reasons other than toxicity and DLT will be replaced.

After 4 cycles of therapy or earlier if clinically indicated, response determination will be assessed by the IMWG criteria. At the end of Cycle 4, if a subject has responded (complete or partial response) or has stable disease, dosing with CT-011, lenalidomide and dexamethasone(if initiated after cycle 1-2) will continue for a minimum of 8 additional cycles or until withdrawal.

For the Phase II portion

Upon determination of the MTD in the phase I portion of this trial, the phase II portion of the study will commence enrollment at the MTD determined in the phase I portion with CT-011 in combination with lenalidomide. In the event that a MTD is not established, safety and tolerability data collected in the Phase I portion of the study will guide decisions on dosing of CT-011 in the phase II trial.

Dexamethasone 40 mg orally weekly may be added if only stable disease after 3 cycles according to the IMWG criteria (section13). Dexamethasone can be reduced to 20 mg based on tolerability or if patient is 70 years or older.

During the phase II portion of this trial, we will not evaluate patients for DLTs as was done in the phase I portion; however, we will use the DLT criteria to identify potential toxicity and tolerability concerns occurring at any cycle to initiate further evaluation to ensure safety of patients. An independent Data and Safety Monitoring Committee will continue oversight of this trial. See Appendix E for details.

